8.6. Information gathering from medical notes, online systems and databases

Information including cancer stage, treatment given (radiotherapy, chemotherapy, biological agent) and response to treatment will be recorded on the CRF as will results of investigations including pathology, blood tests and imaging.

8.7. Handling of imaging data

Once a scan has been performed, images will be anonymised by replacement of all clinical identifiers with the clinical trial number. The anonymised images will be transferred for long term storage in a server within the

University of Oxford. In collaboration with imaging scientists, detailed evaluation of the images will be undertaken to characterise tumour changes with radiotherapy. These evaluations of the tumour will not directly influence the management of the patient in any way. Should new information emerge from the imaging investigations employed in this study that would impact upon the management of the patient (e.g. detection of previously unknown metastatic disease), the patient would be withdrawn from the study and the appropriate clinical team alerted. Radiological measurements of the extent of disease by MRI, CT of the chest, abdomen and pelvis and whole body FDG-PET will also be performed as per routine clinical practice. These routine diagnostic scans and reports as well as radiotherapy planning imaging will be anonymised and stored on the university server as part of the trial record.

8.8. Sample Handling

Blood samples will be collected, labelled and transferred as per the procedure of the Oxford Radcliffe Biobank. The date and time of collection will be recorded on the CRF. Samples will be stored analysed within the timeframe after collection for which the stability in the samples has been validated and found acceptable.

Consent will be requested from all participants for access to NHS biopsies and surgical specimens that have been or will be obtained as part of routine clinical care, either prospectively or retrospectively. Resection specimens may be transferred to an HTA licensed biobank while the study is open to recruitment and up to 24 months from closure of the study to recruitment for possible use in future ethically approved research. Immunohistochemical assessment of the biopsies and resection specimens will be performed. Genetic analyses will be performed in tissue obtained from consenting individuals to study somatic mutation profiles and gene expression profiles of response, with suppression of genes related to heredity. Data relating to genes known to carry heritable information will be discarded and deleted permanently from the raw data. This work is aimed at the discovery of new tissue biomarkers that may complement the novel imaging modalities being developed in this project.

	ASSAY 1	ASSAY 2	ASSAY 3
Purpose of assay	Genomics	Fixation/storage of biopsy/	Fixation/storage of
, ,		resection tissue	biopsy/resection tissue
Assay	Genetic sequencing	Immunohistochemistry	Genetic sequencing
Type of sample	Whole blood	Biopsy/resection tissue	Biopsy/resection tissue
Vials used	10ml EDTA	Standard	Standard
Total volume/visit	40ml	Standard	Standard
Total volume/patient	120ml	Standard	Standard
Timepoints	Pre, during, post	As per clinical standard	As per clinical standard
	treatment		
Clinical	To sample handling/	As per clinical standard or	As per clinical standard or
Handling/Storage/	GCP lab at room	Biobank if transferred	Biobank if transferred
Transport	temperature		
Storage Conditions	-70 ⁰ freezer	As per clinical standard	As per clinical standard
Person Responsible for Chief Investigator		Chief Investigator	Chief Investigator
analysis			
Frequency of analysis	Batch analysis every 5-	Batch analysis every 5-10	Batch analysis every 5-10
	10 patients	patients	patients

8.9. Discontinuation/Withdrawal of Participants from Study

Each participant has the right to withdraw from the study at any time. In addition, the Investigator may discontinue a participant from the study at any time if the Investigator considers it necessary for any reason including:

- Pregnancy
- Ineligibility (either arising during the study or retrospectively having been overlooked at screening)
- Significant protocol deviation
- Significant non-compliance with study requirements
- An adverse event which results in inability to continue to comply with study procedures
- Disease progression which results in inability to continue to comply with study procedures
- Withdrawal of Consent
- Loss to follow up

The treating consultant will be made aware of the participant's withdrawal from the study. The data from that participant may be included for study endpoints if appropriate and at the discretion of the investigator. The participant can be replaced if they do not complete all three MRI scans mandated in this study. Participants may continue on the study without carbogen breathing if this is not tolerated. They may be replaced at the discretion of the Investigator.

The reason for withdrawal will be recorded in the CRF.

If the participant is withdrawn due to an adverse event, the Investigator will arrange for follow-up visits or telephone calls until the adverse event has resolved or stabilised.

8.10. Definition of End of Study

The end of study is the date of the last visit of the last participant.

9. SAFETY REPORTING

9.1. Definition of Serious Adverse Events

A serious adverse event is any untoward medical occurrence that:

- results in death
- is life-threatening
- requires inpatient hospitalisation or prolongation of existing hospitalisation
- results in persistent or significant disability/incapacity
- consists of a congenital anomaly or birth defect.

Other 'important medical events' may also be considered serious if they jeopardise the participant or require an intervention to prevent one of the above consequences.

NOTE: The term "life-threatening" in the definition of "serious" refers to an event in which the participant was at risk of death at the time of the event; it does not refer to an event which hypothetically might have caused death if it were more severe.

9.2. Reporting Procedures for Serious Adverse Events

A serious adverse event (SAE) occurring to a participant should be reported to the REC that gave a favourable opinion of the study where in the opinion of the Chief Investigator the event was 'related' (resulted from administration of any of the research procedures) and 'unexpected' in relation to those procedures. Reports of related and unexpected SAEs should be submitted within 15 working days of the Chief Investigator becoming aware of the event, using the HRA report of serious adverse event form (see HRA website).

9.3. Management of expected adverse events

We do not anticipate any adverse events from the investigational scans. MRI does not require the use of ionising radiation and standard MRI precautions and exclusions will be followed to ensure the safety of study participants.

In terms of supplemental oxygen and carbogen, once contraindications are excluded, the risks of taking part in such experiments are minimal. A researcher will go through a list of possible risks with the participant before the study and answer any questions. Oxygen or carbogen will be delivered through either a breathing mask or a nasal cannula, termed the gas delivery device. The breathing mask is placed over the nose and mouth and secured with a strap behind the head. The nasal cannula consists of a pair of gas outlets that are placed just below the nostrils which are secured by connected tubing that runs over and behind the ears. In both cases, gases are transported via tubing to the gas delivery device. Delivery of gases will be controlled by a system of manual or automated control valves. Recent Cochrane reviews highlight the lack of evidence on either beneficial or detrimental effects of oxygen (27, 28). Within the scope of these findings, breathing of normobaric supplementary oxygen of up to 100% for short periods is considered completely safe both in normal controls and patient groups. The risk of oxygen toxicity would only become of importance beyond 16 hours of oxygen administration and at partial pressures beyond 0.5 bar. MRI scanning of patients breathing supplemental oxygen is clinically routine and standard precautions will be taken. The range of hypercapnia stimuli that will be used in this study is physiological and is experienced repeatedly by most people throughout the day in the course of their lives. Supplemental carbogen breathing can induce the sensation of breathlessness and patients will be warned of this potential effect. During the whole duration of the experiment, the participant is able to talk with the researchers and indicate any discomfort. They will be monitored continuously during supplemental oxygen and carbogen breathing using a gas monitor.

In order to provide contrast for the glucoCEST MRI imaging, participants will be asked to fast for a period of at least six hours prior to intravenous dextrose being administered: 50ml of 50% dextrose bolus followed by 100ml of 10%-20% dextrose over 10-20 minutes, total 45g glucose. If after early analysis the infusion is not required, it will be omitted for future patients. The bolus being given is analogous to that used for the intravenous glucose tolerance test (IVGTT) and the total dose of 45g glucose is within the

range used as part of the IVGTT. The IVGTT has been extensively studied for use in the diagnosis of diabetes mellitus (29, 30) and is not expected to cause significant risk to participants. There have been reports of thrombophlebitis following the peripheral administration of intravenous dextrose and to limit this, cannulation of small veins will be avoided and an 18 or 20 Gauge cannula should be used. All patients will receive a 20ml saline flush immediately following both the dextrose bolus and infusion. Patients with diabetes mellitus type 1 or poorly controlled type 2 diabetes mellitus will be excluded from taking part as will any participant with a confirmed fasting blood sugar of 8mmol/L. Blood sugar levels will be checked before and during the MRI scan as detailed in section 8. If 2 abnormal glucose results are obtained at baseline or the investigator has concerns about proceeding, the patient will not receive the intravenous dextrose. The participant may continue with the remaining MRI sequences & visits at the discretion of the investigator. The administration of intravenous dextrose and blood glucose testing will be done for study purposes only and will not determine patients with previously undiagnosed impaired glucose tolerance or diabetes mellitus. Any concerns will be reported to the patient's GP who may then arrange further investigations.

Gadolinium is in routine clinical use as an intravenous MRI contrast agent. Standard hospital policy will be followed when used in this study. It will not be given to patients with significantly reduced renal function. It can cause side effects but these are usually mild and short-lasting. These include injection site pain, nausea, vomiting, itching, rash, headache and paraesthesia (abnormal skin sensation). If the injection leaks out from the vein into surrounding tissue (extravasation), patients may experience stinging or pain. Allergic reactions are uncommon but can occur. Extravasation and allergic reaction will be managed as per standard hospital policy if they occur.

Participants will be assured that they can withdraw from the study for any reason without penalty.

10. STATISTICS

10.1. Description of Statistical Methods

Descriptive statistics of the patient population will be reported using numbers (with percentages) for binary and categorical variables and means (and standard deviations), or medians (with lower and upper quartiles) for continuous variables. Measurements from the different MRI sequences, FDG-PET scans, immunohistochemistry and genetic expression analyses will be described and the association between them will be assessed using appropriate measures of correlation.

The primary outcome measure is to assess percentage change from baseline in T1 and T2* during and post RT, with supplemental oxygen. Secondary outcomes measures include the percentage change in CEST signal with the addition of supplemental oxygen and carbogen, the percentage change in T1 and T2* with supplemental carbogen and the percentage change in glucoCEST signal with intravenous glucose. Changes in GlucoCEST signal with treatment will be compared to changes in DCE-MRI parameters, including ktrans, and FDG-PET parameters, including SUVmax. In Group B, we will be testing intra-patient agreement between sequential scans. The Bland-Altman test will be used to quantify the degree of agreement between the imaging parameters derived from the different sequences. There are no planned interim statistical analyses.

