2. SYNOPSIS

Study Title	Biological Magnetic Resonance Imaging Parameters in oropharyngeal squamous cell carcinoma			
Short Title	BIOPIC			
Rationale:	Imaging is a vital component of the head and neck cancer management pathway. Magnetic Resonance Imaging (MRI) is used routinely to provide anatomical assessment and with the emergence of novel techniques may be used for imaging physiological processes. This study will focus on MRI with supplemental oxygen/carbogen breathing and assessment of exogenous and endogenous contrast agents with Chemical Exchange Saturation Transfer (CEST) MRI in patients undergoing radical dose radiotherapy. Multiparametric tissue characterisation with MRI has potential for use in adaptive radiotherapy planning, to assess the effects of treatment and evaluate the actions of targeted therapies.			
Study Design	Observational			
Study Participants	Patients with HPV positive oropharyngeal squamous cell carcinoma undergoing radical radiotherapy.			
Sample Size	20			
Follow-up	3 months			
	Objectives	Outcome Measures		
Primary	Assess changes in tumour T1 & T2* imaging with supplemental oxygen during and after radiotherapy	Changes from baseline in T1 & T2* signal during and post RT with supplemental oxygen		
		Changes from baseline in CEST signal during and post RT with and without supplemental oxygen		
	Assess changes in tumour T1/T2* & CEST imaging with supplemental carbogen during and after radiotherapy	Changes from baseline in T1, T2* and CEST signal during and post RT with supplemental carbogen		
	Assess changes in CEST imaging with treatment	Changes from baseline during week 2 RT and 10 weeks post RT		
	- GlucoCEST levels pre & post glucose l			
		- Markers such as Choline, creatine, lactate, APT		

	Assess whether glucoCEST imaging correlates with FDG-PET parameters	Compare glucoCEST levels with FDG-PET parameters including SUVmax & uptake volume at baseline & 10 weeks post RT
	Compare dynamic contrast enhanced MRI with dynamic glucoCEST	Standard DCE-MRI parameters (e.g. ktrans, Kep, Ve, AUC) will be compared with dynamic glucoCEST signal changes (e.g. AUC).
	Evaluate the consistency of MRI parameter measurements	Test-retest imaging at baseline in subgroup of participants
Exploratory	Compare imaging findings with histopathology	Immunohistochemistry and genetic markers including CAIX, Ki-67 and GLUT-1. Other markers such as those related to hypoxia, proliferation, radioresistance and metabolism will be explored.

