Intravenous dextrose will be given for no more than 20 minutes. Participants will have an intravenous bolus injection of 50ml 50% (0.5g/ml) dextrose solution by a 20ml saline flush. They will then have up to a 20 minute infusion of 10%-20% dextrose solution followed by a further 20ml saline flush. The infusion may be reduced or omitted if early analysis suggests it is not required. Participants will be asked to inform research staff immediately if the cannula becomes uncomfortable or painful. Blood glucose testing using a hand-held blood glucose monitoring device will be done either by sampling through the cannula in the contralateral arm or hand to that used for contrast injection or through finger prick testing. Blood sampling will be undertaken once prior to MRI (twice if the first result was out of the expected range) and up to four times during the MRI on each scan visit.

Visit 3: Baseline MRI 2 (Group B only)

Group B participants will have a second baseline scan at least 48 hours following the first, for test-retest purposes. A blood test will be taken at this visit if not done at visit 2.

Visit 4: On treatment MRI & blood test

On fraction 10+/-2 of radiotherapy. Prior to radiotherapy that day where possible. The MRI and blood test will be undertaken as on Visit 2 (baseline).

Visit 5: Post-treatment MRI & blood test

To coincide with routine post-treatment imaging where possible. The MRI and blood test will be undertaken as on Visit 2 (baseline).

The patient's participation in the study will end following their post-treatment MRI or at time of radical surgery if they proceed to resection (expected only in a minority of cases).

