10.2. The Number of Participants

20 patients will be recruited in total. 15 patients will be recruited into Group A and 5 patients will be recruited into group B and undergo two baseline scans. This sample number has been chosen to give reasonable assessment of the endpoints in this observational study exploring novel MRI techniques in radiotherapy within a reasonable time frame. The results from this study will be used to plan future studies.

Based upon projected accrual rates, this study is expected to complete recruitment within 18 months of opening to recruitment. Patients who do not complete the study may be replaced if within the planned recruitment period at the discretion of the Chief Investigator.

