10.3. Analysis of Outcome Measures

Primary and secondary outcomes will be analysed as described in section 10.1. Data from group A patients will be analysed for all endpoints except the secondary endpoint related to test-retest imaging. Data from group B participants will be used to address all endpoints. All participants will be included in the analysis of data, whether or not they undergo all of the planned imaging studies.

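### Section 10.1 as worded applies Bland-Altman to parameters from different sequences, which are different quantities; it should name the same parameter at the two Group B baseline scans

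*Protocol*

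**What the plan says.** The synopsis lists consistency of the MRI measurements as an objective, with the outcome measure "Test-retest imaging at baseline in subgroup of participants". Section 8.5 schedules the repeat scan as Visit 3: "Group B participants will have a second baseline scan at least 48 hours following the first, for test-retest purposes". Section 10.2 sets the size: "15 patients will be recruited into Group A and 5 patients will be recruited into group B and undergo two baseline scans". Section 10.3 confines the endpoint to Group B: "Data from group A patients will be analysed for all endpoints except the secondary endpoint related to test-retest imaging". It also refers back to 10.1 for the analysis of primary and secondary outcomes.

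Section 10.1 contains three statements that bear on the method:

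- For measurements from the MRI sequences, FDG-PET, immunohistochemistry and genetic expression, "the association between them will be assessed using appropriate measures of correlation".
- "In Group B, we will be testing intra-patient agreement between sequential scans". No method is named in this sentence.
- The next sentence: "The Bland-Altman test will be used to quantify the degree of agreement between the imaging parameters derived from the different sequences".

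The protocol does not say how limits of agreement are to be calculated.

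**The concern.** A Bland-Altman analysis takes the difference between two measurements of the same quantity in each patient and describes the spread of those differences. It is suited to one parameter measured at Visit 2 and again at Visit 3. Taken at its word, the sentence asks for it between parameters from different sequences, where a difference generally has no meaning.

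An analyst who follows the text literally would produce limits that cannot be interpreted as agreement. An analyst who does the sensible test-retest analysis would depart from the text. Group B patients attend for an extra scan solely for this endpoint, so the protocol should state the analysis plainly before the data are seen.

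**Working it through.** **What the sequences measure.** Section 8.5 lists eleven acquisitions, including diffusion, T1/T2*, CEST, spectroscopy and DCE-MRI. The synopsis names ktrans, Kep, Ve and AUC for DCE-MRI, and signal change for dynamic glucoCEST. These are different quantities. Two special cases do not rescue the literal reading:

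- Several outcomes in 10.1 are percentage changes and so have no unit. A percentage change in T1 and one in CEST signal still describe different things.
- The list in 8.5 counts T1/T2* on air, with oxygen and with carbogen as separate items. The same parameter under two gases can be subtracted, but the difference is then the gas response that the study sets out to measure, not a disagreement between measurements.

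**How 10.1 uses the term.** The opening paragraph of 10.1 refers to the different MRI sequences in the ordinary sense, as distinct acquisitions, and gives their relations to correlation. Reading the Bland-Altman sentence in the same sense assigns those relations a second and unsuitable method, and leaves the Group B sentence without one.

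**Sample size.** The stated total is reproduced: 15 + 5 = 20. Section 10.2 gives no power or precision calculation, so nothing further can be reproduced.

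**Precision with 5 pairs (supporting point).** Inputs: n = 5 pairs from 10.2, so 4 degrees of freedom. Normally distributed differences are assumed. The 1.96 multiplier is also an assumption, being the usual default and not in the protocol.

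1. Average coverage of a new difference by mean ± 1.96 SD is P(|t₄| < 1.96/√(1 + 1/5)) = P(|t₄| < 1.789) = 0.852. One million simulated samples of five also gave 85.2% on average. Coverage fell below 95% in 67% of the samples and below 80% in 28%.
2. The multiplier for a 95% prediction interval is t(0.975; 4) × √1.2 = 2.776 × 1.095 = 3.04. Relative to 1.96 this is 3.04/1.96 = 1.55.
3. The 95% confidence interval for the SD of differences, as a multiple of its estimate, is √(4/χ²) at the 0.975 and 0.025 quantiles: 0.60 to 2.87.
4. The exact 95% confidence interval for the upper limit, from the noncentral t distribution, runs from mean + 0.92 SD to mean + 5.98 SD.
5. For comparison, average coverage as in step 1 would be 90.6% with 10 pairs and 92.9% with 20.

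Section 8.5 lets investigators omit any sequence, so some parameters may have fewer than 5 pairs.

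**The case against.** The best answer is that the two adjacent sentences belong together: the first gives the comparison (sequential scans in Group B) and the second gives the method, applied to the parameters that each sequence yields. Since correlation is already assigned to cross-sequence relations, this is probably what the authors meant. That stands, and it lowers the severity. It does not remove the point. The sentence as written places the agreement between sequences, nowhere mentions the two baseline scans, and uses a term that has its cross-sequence sense earlier in the same section. The planned comparison of glucoCEST with DCE-MRI keeps the literal reading open.

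A second answer is that the calculation of the limits can be left to a statistical analysis plan. That also stands. A reader might infer that the protocol prescribes limits that are too narrow, but it prescribes none. A reader might also take 3.04 as the one correct multiplier. It answers one question, where a new difference will fall. Conventional limits estimate population limits; as such they are only about 6% too narrow on average at n = 5 (the expected sample SD is 0.94 of the true value), and reporting them with confidence intervals is legitimate. Most of the shortfall in coverage comes from having 5 pairs, which no rewording cures.

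A third answer is that little depends on this endpoint. It is secondary, in a 20-patient observational study meant to help plan later ones. This too is fair.

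**Conclusion.** The point holds as a fault in a stated analysis. Section 10.1 attaches Bland-Altman to a comparison for which it does not measure agreement, and the probable intention, test-retest in Group B, has to be guessed from the sentence before. Severity is minor to moderate.

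The figures of 85% and of 0.60 to 2.87 are conditional: they assume normal differences and all 5 pairs, and the 85% also assumes the default 1.96 multiplier. They show that any limits from this subgroup will be imprecise, not that the protocol has miscalculated.

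Two stronger readings are not supported:

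- That all the parameters differ in units. The protocol states no units, T1 and T2* are both times, and percentage changes have none. The sound objection is that the quantities differ.
- That faulty limits would cause noise to be read as a treatment effect. Repeatability would be a natural reference for judging change, but the protocol sets no rule that compares an individual's change with it, and the primary outcome is analysed separately.

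**What to change.** Replace the Bland-Altman sentence in section 10.1 with wording such as:

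> In Group B, Bland-Altman analysis will be used for each imaging parameter separately, and for each gas or glucose condition, to quantify agreement between the first and second baseline scans (Visit 2 versus Visit 3). The mean difference, within-patient SD, repeatability coefficient and limits of agreement will be reported with small-sample confidence intervals. Relations between different sequences will be assessed by correlation.

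Add that these results are exploratory and that the number of pairs will be given for each parameter. Calling the method an analysis also avoids the word test, since it estimates agreement. The choice of limit formula can stay with the statistical analysis plan, provided that it suits 5 pairs and is fixed before the Group B data are analysed.

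The cost is one sentence. No scan, visit, patient or data item is added, and the primary analysis is unchanged. The reported intervals will be wide, which is a fair picture of what 5 pairs can show.
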